## 19.6 Demographic and Baseline Characteristics

Subject demographics, medical history, previously failed AADs (if any), active AAD use (still administered) and other baseline data will be summarized descriptively for all enrolled subjects.

## 19.7 Endpoints and Associated Hypotheses

### 19.7.1 Primary Safety Endpoint:

To evaluate the primary safety objective of the study, the PAE rate will be formally compared against a performance goal of 12%.

The null and alternative hypotheses are:

$H_0: P_S \geq 0.12$  vs.  $H_A: P_S < 0.12$ ,  
where  $P_S$  denotes the rate of early onset Primary Adverse Events

### 19.7.2 Primary Effectiveness Endpoint:

The null and alternative hypotheses are:

$H_0: P_E \leq 0.90$  vs.  $H_A: P_E > 0.90$ ,  
where  $P_E$  denotes the rate of acute effectiveness success

### 19.7.3 Secondary Effectiveness Endpoint:

The null and alternative hypotheses are:

$H_0: P_1 \leq 0.50$  vs.  $H_A: P_1 > 0.50$ ,  
where  $P_1$  denotes the proportion of freedom from secondary effectiveness failures at 12 months post the initial ablation procedure.

## **19.8 Analyses to be Conducted.**

### **19.8.1 Primary Safety Endpoint**

The number and percentage of primary safety events will be reported. The hypothesis testing of the primary safety endpoint will be based on 3-month follow-up data. The primary safety endpoint will be evaluated using an exact test for a binomial proportion at a one-sided significance level of 2.5%. If the upper bound of the exact two-sided 95% confidence interval of the primary safety endpoint rate is less than the performance goal of 12%, the study will be considered to have demonstrated safety. The primary safety endpoint analysis will be performed in the mITT analysis set.

### **19.8.2 Primary Effectiveness Endpoint**

The number and percentage of acute effectiveness success will be reported. The acute effectiveness endpoint will be evaluated using the exact test for a binomial proportion at a one-sided significance level of 2.5%. If the lower bound of the exact two-sided 95% confidence interval of the acute effectiveness success rate is greater than the performance goal of 90%, the study will be considered to have demonstrated effectiveness. The primary effectiveness endpoint will be performed in the Per Protocol analysis set.

The study will be declared a success if both primary safety and acute effectiveness endpoints are met. A CSR will be submitted when all subjects completing 3 months of follow-up. The hypothesis of the secondary endpoint will be tested based on the 12-month follow-up data, only if the primary endpoints are met.

### **19.8.3 Secondary Effectiveness Endpoint**

The secondary effectiveness endpoint of 12-month recurrence-free rate will be evaluated using the Kaplan-Meier estimate. The proportion for freedom from effectiveness failure events at 12-month, along with the two-sided 95% confidence interval, will be estimated. If the lower bound of the confidence interval is greater than the performance goal of 50%, the study will be considered to have demonstrated long-term effectiveness of the study system. Acute procedural failure (i.e., failure to confirm entrance block with or without touch-up in all PVs except those that are silent and/or cannot be cannulated post procedure) will also be deemed an effectiveness failure.

The 12-month effectiveness success analysis will be performed in the PP analysis set. However, per section 13.3 and 13.4, using a commercial RF device for the treatment of arrhythmia outside the PV region, such as for the ablation of a CTI line for documented typical AFL identified prior to or during the procedure, is allowed during index or within-blanking repeat ablation procedure. To filter out the potential effect of the commercial RF devices on the long-term effectiveness, these subjects will be censored at the time of using the commercial RF device for this 12-month effectiveness analysis.

If success is achieved in both the primary safety and acute effectiveness endpoints, then the secondary effectiveness endpoint will be tested. The secondary hypothesis test will be performed after all subjects have completed their 12-month follow up. The testing of the hypothesis for the secondary effectiveness endpoint after the success of the primary endpoints are met ensures family-wise error rate is controlled at a 2.5% level.

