### **7.4.3 Additional Effectiveness Endpoints**

**PVI Durability (for PVI Durability subset):** defined as a sustained isolations of PVs that are targeted in the index ablation procedure, which is evidenced by the confirmation of isolation via the electroanatomical mapping 75 days (+/- 15 days) post index ablation procedure.

**Single Procedural Success:** defined as freedom from documented symptomatic atrial arrhythmia (AF, AT or AFL of unknown origin\*) episodes based on electrocardiographic data ( $\geq 30$  seconds on arrhythmia monitoring device) during the effectiveness evaluation period (day 91-day 365) following a single index ablation procedure.

**Freedom from documented symptomatic atrial arrhythmia** (AF, AT or AFL of unknown origin\*) episodes based on electrocardiographic data ( $\geq 30$  seconds on arrhythmia monitoring device) during the effectiveness evaluation period (day 91-day 365). Acute procedural failure will also be considered failure of 12-month symptomatic recurrence free endpoint.

**Freedom from documented (symptomatic and asymptomatic) atrial arrhythmia** (AF, AT or AFL of unknown origin\*) episodes based on electrocardiographic data ( $\geq 30$  seconds on arrhythmia monitoring device) during the effectiveness evaluation period (day 91-day 365) **with extra failure modes**. A subject who meets any of the following criteria will also be deemed an effectiveness failure:

- Failure to achieve acute procedural success.
- Taking a new Antiarrhythmic Drug (AAD) (Class I / Class III) for atrial tachyarrhythmia (AF, AT or AFL of unknown origin\*) or taking a previously failed Class I/III AAD at a greater than the highest ineffective historical dose for AF/AFL/AT during the effectiveness evaluation period (day of 3-month visit – day 365).
- Greater than 1 repeat ablation for AF/AT or AFL of unknown origin\* in the blanking period or any repeat ablation for AF/AT or AFL of unknown origin\* during the effectiveness evaluation period.

**Use of a non-study device** for the purpose of:

- PVI (i.e., touch-up) among all clinically relevant targeted PVs during index ablation procedure.
- Ablation of left atrial non-PV AF targets (i.e., posterior wall) during index ablation procedure or for repeat procedures during blanking period.

**Acute reconnection** identified by adenosine/isoproterenol challenge among all clinically relevant targeted PVs.

[figure not shown]

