#### During the blanking period:

- Repeat procedures during the blanking period ( $\leq 90$  days post index ablation procedure) must be conducted with the investigational device, with or without focal touch-up, if the arrhythmia is due to PV triggers. ONLY after investigator deems unable to achieve PVI with the investigational device, a commercial and compatible BWI (RF) system can be used to complete the procedure (PVI only).
- If the arrhythmia is due to non-PV triggers and the subject is treated with a commercially available ablation catheter and generator, the subject will be excluded from the long-term effectiveness cohort.
- Procedures for newly CTI dependent flutter in the follow up period are not considered repeat procedures per CIP and will be treated with a commercially available ablation catheter and generator.

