- Additional Assessments for **PVI Durability subset** subjects (non-SOC):
  - A repeat electro anatomical creation of a paced activation map and bipolar voltage map will be performed at 75 days (+/-15days) post index ablation procedure to verify isolation durability of the treated pulmonary vein during the index ablation procedure.
  - A BWI multi-electrode mapping catheter should be used for the remap procedure. It is **REQUIRED** to use the same mapping catheter that was used during the index ablation procedure.
  - If reconnections are identified in the remap procedure, additional ablations may be performed at the discretion of the investigator with the investigational ablation system. If the additional ablations cannot be achieved with the investigational system, a commercially approved and compatible BWI RF catheter and generator should be used.

- **Quality of life** via the Atrial Fibrillation Effect on Quality-of-Life (AFEQT™) questionnaire (non-SOC), at Month 3, 6 and 12. NOTE: Patient questionnaires will only be used in countries with validated languages.

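### Protocol 19.8.3 words acute failure for the 12-month test more loosely than the endpoint definition if touch-up means a non-study device, and its readable censoring rule does not cover commercial RF used on the PVs after the index procedure.

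*Protocol*

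**What the plan says.** The 12-month endpoint is tested against 50% by Kaplan-Meier in the PP set, and only if both primary endpoints are met (Protocol 19.8.2, 19.8.3; SAP 7.10).

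**Acute failure.** An acute procedural failure is also a 12-month failure. Protocol 7.4.2 and SAP 7.4.3 define it as not achieving entrance block with the study device. Protocol 7.4.1 and SAP 7.4.2 add that using a non-study device to achieve PVI is an acute failure. Protocol 19.8.3 words it differently: "failure to confirm entrance block with or without touch-up in all PVs except those that are silent" or cannot be cannulated.

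**Commercial RF.** 19.8.3 then addresses "using a commercial RF device for the treatment of arrhythmia outside the PV region" at the index procedure or a within-blanking repeat. Its purpose is given as "To filter out the potential effect of the commercial RF devices on the long-term effectiveness", and its rule is that "these subjects will be censored at the time of using the commercial RF device for this 12-month effectiveness analysis".

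**Other permitted RF before Day 91.** Two other places allow commercial RF on the PVs:
- Section 13.4, at a blanking-period repeat, once the investigator judges that the study device cannot achieve PVI: "a commercial and compatible BWI (RF) system can be used to complete the procedure (PVI only").
- Section 13.5.2, at the remap of the 30 durability subjects, 75 ± 15 days after the index procedure: "If the additional ablations cannot be achieved with the investigational system, a commercially approved and compatible BWI RF catheter and generator should be used".

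**The concern.** Two things in 19.8.3 bear on who counts as a 12-month success.

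First, a tested endpoint has two descriptions of one failure mode. Under the looser one, a subject whose veins were isolated at the index only with help from a commercial RF catheter would fail the acute endpoint yet could succeed at 12 months. The censoring sentence would not catch that subject either, because the RF was on the PVs.

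Second, RF away from the PVs leads to censoring, while the readable text has no rule for RF on the PVs after the index procedure. No other readable rule for this endpoint fills the space. Acute failure is tied to the index procedure, and repeat ablation is a failure mode only of additional endpoints. A subject re-isolated with commercial RF before Day 91 and free of episodes on Days 91-365 can therefore count as a success of the study device.

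At stake is the only hypothesis-tested long-term claim.

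**Working it through.** **Inputs.** 135 evaluable main-study subjects (Protocol 19.2); 12-month goal 50% and acute goal 90%, each judged by a two-sided 95% lower bound (19.8.2, 19.8.3); 30 remap subjects (7.3.4), which is 30/135 = 22%. The assumptions behind 135 are redacted, so that figure cannot be reproduced.

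**Assumptions.** The PP set has 135 subjects, nobody else is censored, and the limit is the plain one. Kaplan-Meier then reduces to a proportion, with lower bound LB = p − 1.96·√(p(1−p)/n). The number of subjects given RF on the PVs after the index procedure, k, is not in the documents; 3 is assumed, with a range of 1 to 6.

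**Pass mark.** 79/135 = 58.5%, LB = 0.5852 − 1.96·√(0.5852·0.4148/135) = 50.2%, passes. 78/135 = 57.8%, LB 49.5%, misses. On a log-log limit the mark is 80/135 (LB 50.5%; 79/135 gives 49.7%).

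**Part 1: how many subjects the acute wording can move.** The 12-month test runs only if the acute goal is met. By the exact (Clopper-Pearson) limit, 129/135 has LB 90.6% and passes; 128/135 has LB 89.6% and misses. So at most 135 − 129 = 6 subjects can be acute failures when the test runs, and the wording can move at most 6/135 = 4.4 points. At that maximum, 82 recurrence-free including 6 index touch-ups gives:
- counted as successes: 82/135 = 60.7%, LB 52.5%, pass;
- counted as failures: 76/135 = 56.3%, LB 47.9%, miss.

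**Part 2: RF on the PVs after the index procedure, k = 3.**

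| Case | Kept | Censored before Day 91 | Failed |
|---|---|---|---|
| 80 recurrence-free, including all 3 | 80/135, LB 51.0% | 77/132, LB 49.9% | 77/135, LB 48.7% |
| 78 recurrence-free, all 3 recur | 78/135, LB 49.5% | 78/132, LB 50.7% | 78/135, LB 49.5% |

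In the first row, keeping these subjects turns a miss into a pass. In the second, censoring does so.

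**Where the verdict changes.** Counts are recurrence-free subjects out of 135 when everyone is kept, found by applying the same formula to each count.

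| k | Kept vs censored, all k recurrence-free | Kept vs failed, all k recurrence-free | Kept vs censored, all k recur |
|---|---|---|---|
| 1 | 79 | 79 | none (78/134, LB 49.9%) |
| 3 | 79-80 | 79-81 | 78 |
| 6 | 79-81 | 79-84 | 76-78 (76/129, LB 50.4%) |

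Across the range the verdict is at risk only between 76/135 = 56.3% and 84/135 = 62.2%.

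**The case against.** **Redaction.** The gap in Part 2 is an absence, and the places where a rule would sit are blacked out: the PP definition in both documents, part of SAP 7.1, SAP 7.8.3 and the core of SAP 7.10. Protocol 19 also calls itself a brief overview. This stands. A reader might infer that the plan has no rule for RF on the PVs and will credit it to the study device; the documents support only that no readable rule covers it.

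**The aim may be narrow.** The sentence about filtering out commercial RF follows directly on one about RF outside the PV region, so the rule may be exactly as wide as its purpose. This stands too: the rule cannot be said to contradict its own aim.

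**Keeping such subjects may be intended.** Recurrence in blanking is not a failure (Appendix 1), and the endpoint with extra failure modes tolerates one blanking-period repeat. Whether to keep, censor or fail these subjects is partly a choice of estimand. That argues for leaving the main analysis alone, not for leaving the question unexamined.

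**Touch-up may be innocent.** In 13.4, a blanking-period repeat "must be conducted with the investigational device, with or without focal touch-up, if the arrhythmia is due to PV triggers", and RF appears there as a separate fallback. On that reading touch-up is further study-device energy and 19.8.3 is not looser. But under use of a non-study device, 7.4.3 lists "PVI (i.e., touch-up) among all clinically relevant targeted PVs during index ablation procedure", and 19.8.5 uses the term the same way. Both readings are available, which is reason enough to settle the text. A reader might also infer that 19.8.3 is looser in every respect. It is not: on which veins count, its wording differs from the other definitions but is not clearly weaker.

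**Conclusion.** The acute-failure wording in 19.8.3 should be corrected. It conflicts with the readable definition of the same tested endpoint when touch-up carries its 7.4.3 meaning, and no hidden text can remove a conflict between two readable passages. Its reach is at most 6 of 135 subjects.

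The RF point is narrower: the readable censoring sentence leaves out RF on the PVs after the index procedure and before Day 91. A reader might infer that this inflates the 12-month rate. The documents do not support a direction: keeping these subjects helps the device if they stay free of arrhythmia and hurts it if they recur. The verdict is exposed only near the pass mark, under the assumptions of n=135, a plain limit, no other censoring and k between 1 and 6. Commercial ablation after Day 90 is not sized here.

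Section 13.4 says excluded where 19.8.3 says censored for non-PV RF in blanking. That is not a numerical concern: the lower bounds are identical with no acute failures.

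Study success rests on the two primary endpoints and is unaffected.

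**What to change.** 1. In Protocol 19.8.3, replace the acute-failure parenthesis with the wording of Protocol 7.4.2 and SAP 7.4.3: entrance block must be achieved with the study device, and a non-study device used for PVI at the index procedure is a failure.
2. Leave the main 12-month analysis as planned. In SAP 7.10, prespecify one sensitivity analysis that counts commercial RF on the PVs, used after the index procedure and before Day 91, as a failure from the time of use. This is preferable to widening the censoring rule: censoring after a reconnection may be informative and, as shown, can turn a miss into a pass.
3. Confirm that both changes agree with the redacted PP definition and SAP 7.1, 7.8.3 and 7.10.

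The cost is one wording change and one extra analysis. The sensitivity rate can only equal or fall below the main rate, so it may look less favourable.

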#### 19.8.4 Subgroup Analyses

Subgroup analyses by clinically relevant factors will be performed and details will be provided in SAP.

#### 19.8.5 Additional Endpoint Analyses

No formal statistical hypotheses will be formulated and performed for the additional endpoints. Additional safety endpoints will be analyzed in SP, and mITT analysis sets. Effectiveness endpoints and procedural data will be analyzed in the PP and mITT analysis sets respectively. NA, EE, CT/MRA, and PVI durability endpoints will be analyzed in the NA, EE, CT/MRA, and PVI durability analysis sets, correspondingly. All endpoints will also be analyzed for the roll-in analysis set separately. Details of the analyses will be elaborated in the SAP.

- **PVI Durability Rate (for PVI Durability subset)**
  - Percentage of targeted PVs in the index ablation procedure being durably isolated as confirmed by the electroanatomical mapping 75 days (+/- 15 days) post index ablation procedure.
  - Percentage of subjects with durably isolated targeted PVs, as confirmed by the electroanatomical mapping at 75 days (+/- 15 days) post index ablation procedure.
  
- **Single Procedural Success:** defined as freedom from documented symptomatic atrial arrhythmia (AF, AT or AFL of unknown origin\*) episodes based on electrocardiographic data ( $\geq 30$  seconds on arrhythmia monitoring device) during the effectiveness evaluation period (day 91-day 365) following a single index ablation procedure. CCI  
[REDACTED]
  
- **Freedom from documented symptomatic atrial arrhythmia** (AF, AT or AFL of unknown origin \*) episodes based on electrocardiographic data ( $\geq 30$  seconds on arrhythmia monitoring device) during the effectiveness evaluation period (day 91-day 365). Acute procedural failure will also be considered failure of 12-month symptomatic recurrence free endpoint. The proportion of freedom from documented symptomatic atrial arrhythmia at 12 months post the index ablation procedure will be evaluated using the Kaplan-Meier estimate.
  
- **Freedom from documented (symptomatic and asymptomatic) atrial arrhythmia** (AF, AT or AFL of unknown origin\*) episodes based on electrocardiographic data ( $\geq 30$  seconds on arrhythmia monitoring device) during the effectiveness evaluation period (day 91-day 365) **with extra failure modes**. A subject who meets any of the following criteria will also be deemed an effectiveness failure:
  - Failure to achieve acute procedural success.
  - Taking a new Antiarrhythmic Drug (AAD) (Class I / Class III) for atrial tachyarrhythmia (AF, AT or AFL of unknown origin\*) or taking a previously failed Class I/III AAD at a greater than the highest ineffective historical dose for AF/AFL/AT during the effectiveness evaluation period (day of 3-month visit – day 365).
  - Greater than 1 repeat ablation for AF/AT or AFL of unknown origin\* in the blanking period or any repeat ablation for AF/AT or AFL of unknown origin\* during the effectiveness evaluation period.

The proportion of freedom from documented symptomatic atrial arrhythmia and extra failure modes at 12 months post the index ablation procedure will be evaluated using the Kaplan-Meier estimate.

- **Use of a non-study device** for the purpose of PVI (i.e., touch-up) among all clinically relevant targeted PVs during the index procedure and/or ablation of left atrial non-PV AF targets (i.e., posterior wall) during index ablation procedure or for repeat procedures during blanking period will be summarized descriptively by the purposes of use, timing of use, at the subject-level and at the vein-level, if applicable.
- **Acute reconnection** identified by adenosine/isoproterenol challenge among all clinically relevant targeted PVs will be summarized descriptively at the subject-level and at the vein-level.
- **Repeat ablation procedures** for left atrial arrhythmia (AF, AT or AFL of unknown origin\*) within the 12-month FU period will be summarized descriptively for the following:
  - Percentage of subjects with repeat ablation during blanking period ( $\leq 90$  days post index ablation procedure).
  - Percentage of subjects with repeat ablation after blanking period (day 91 – 365 post index ablation procedure).
  - Percentage PV reconnection observed during repeat ablation procedures by targeted PVs treated at index ablation procedure and by subject.
  - Percentage of subject with repeat ablations due to non-PV targets.
- **Quality of Life (QoL)**: the change of QoL assessed by comparing the Atrial Fibrillation Effect on Quality-of-Life (AFEQT™) scores before and at 3, 6 and 12- months after the ablation procedure will be summarized descriptively in subjects with non-missing data.
- **Hospitalization for cardiovascular events** through 12 months follow-up compared to 12 months prior to baseline.

CCI

The proportion of freedom from cardiovascular events-related hospitalization at 12 months post the index ablation procedure will be evaluated using the Kaplan-Meier estimate. The change of cardiovascular events-related hospitalization between 12-month before and after the index procedure will be summarized descriptively, in terms of the percent of subjects with event, average length of stay.

- **Safety**
  - Occurrence of Serious Adverse Device Effects (SADEs)
  - Occurrence of Unanticipated Serious Adverse Device Effects (USADEs)
  - Occurrence of Serious Adverse Events (SAEs) within 7 days (early-onset), 8 to 30 days (peri-procedural) and >30 days (late onset) of index ablation procedure
  - Occurrence of non-serious adverse events (non-SAEs)

- **Neurological Assessment Subset**
  - Occurrence of new post-ablation asymptomatic and symptomatic cerebral emboli observed post-ablation as determined by Magnetic Resonance Imaging (MRI) evaluations will be summarized by the anatomical location. The size of the lesions will be listed for individual events.
  - Incidence of new or worsening neurological deficits post-ablation and at follow-up, compared to baseline.
  - Mini Mental State Examination (MMSE), National Institute of Health Stroke Scale (NIHSS) and Modified Rankin Scale (mRS) will be summarized descriptively for the evaluation at baseline, post-ablation and during follow-up (if lesions were identified in prior evaluation).
- **CT/MRA Subset**
  - Occurrence of PV stenosis up to 3 months post-ablation as determined by Computed Tomography (CT)/ magnetic Resonance Angiogram (MRA) evaluations.
- **Esophageal Endoscopy Subset**
  - Occurrence of endoscopically detected esophageal thermal lesions in the region of the contact area between esophagus and LA as determined by post procedure endoscopy.

Note: *\*AFL of unknown origin is defined as all AFL except those CTI dependent AFL as confirmed by 12-lead electrocardiogram (ECG) or entrainment maneuvers in an EP study.*

